App Measure Selection: The preliminary usability and acceptance of the Salty app was measured to ensure alignment with the latest guidelines for feasibility trials while still addressing the core objective of evaluating the intervention for primary care patients with chronic pain. As part of this measurement selection, the mHealth App Usability Questionnaire (MAUQ) was used to measure preliminary usability, replacing the originally proposed Weiner and colleagues (2017, <https://implementationscience.biomedcentral.com/articles/10.1186/s13012-017-0635-3>) usability measure, due to its strong psychometric evidence and better alignment with construct definitions of evaluating a mobile app. Namely, the MAUQ provided a more robust evaluation of app usability, compared to the originally proposed measure. The MAUQ, the SaltyChP (i.e., a custom built measure developed by 2Morrow Inc. to help evaluate usability for product development and support marketability), and descriptives of app usage (i.e., total number of intervention arm patients that successfully engaged use of the app; days the app was used / proportion of days used that were possible; and, total number of badges earned out of the four that were possible) were used to evaluate preliminary usability and acceptance.

Aim 2. To assess feasibility of recruitment, study uptake, and completion of study assessments.

Feasibility Measure Selection: In alignment with standard measures used in feasibility randomized controlled trials, the following feasibility indicators were selected to assess recruitment procedures, retention, outcome measures' adequacy, and feasibility of implementing the intervention (i.e., Salty app):

1. Recruitment procedures: Ability to recruit a diverse sample of participants with various chronic pain diagnoses and exploring the reasons for ineligibility or study decline.
2. Retention: Will participants stay engaged in the study? Survey completion rates by arm and timepoint.
3. Outcomes measures adequacy: a) Are the measures acceptable, appropriate and relevant to the target population? b) Is there evidence of reliability and validity (including responsiveness to change) of measures in the target population?
4. Intervention implementation: a) Was the intervention delivered as intended? b) Were participants engaged with the program components?

Aim 3. To estimate the likely treatment efficacy effect size for a large RCT.

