Data was collected at baseline (T0), 1-month (T1), 3-month follow (T2), and at 6-month follow up (T3) via REDCap which is a secure, HIPAA-compliant web-based application used for data capture and management. Automatic survey invitation emails were programmed in REDCap to be emailed to participants at each study time point. In these automatic emails, participants were asked to complete surveys via a personalized REDCap survey link. They had two weeks to complete each survey. During the two-week data collection window, follow-up for participants who had not yet completed their surveys could include automatic REDCap email reminders (up to two) and a reminder call and/or email from the study team. Participants could return to their surveys using their personalized survey link at any time during the data collection window. Time spent completing surveys was not recorded. The surveys utilized REDCap enhanced radios and checkboxes for a better user experience across different devices (laptops, tablets, and mobile phones). Participants received a \$50 e-gift card for each survey they completed, up to \$200 total for the entire study. REDCap survey settings allowed participants to skip some questions. In accordance with IRB requirements, participants were not obligated to answer any questions they felt uncomfortable with; as a result, the REDCap survey was configured to allow optional responses. For the purposes of statistical analysis, only complete data sets were included for each outcome measure. Specifically, if a participant omitted any subscale items necessary to calculate a total score, their data were excluded from the summary statistics and analyses for that measure.

The data were extracted from REDCap at the completion of the study for data analyses. No identifiers were maintained, and data were stored using a password protected delimited file and stored in an access-controlled location on a secure HIPAA-compliant server at UW. 2Morrow gave UW usability data logged by their platform. UW linked the 2Morrow usability data to de-identified study identifiers, links to identifiers were then destroyed, and stored similarly to the REDCap derived data.

Outcome measures

(Appendix 1 includes a copy of all outcome measures)

Intervention and Control Group

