your day-to-day activities?					
your enjoyment of recreational activities?					
doing your tasks away from home (e.g., getting groceries, running errands)?					

	Never	Rarely	Sometimes	Often	Always
How often did pain keep you from socializing with others?					

Over the last 2 weeks, how often have you been bothered by any of the following problems?

	Not at all	Several days	More than half the days	Nearly every day
Little interest or pleasure in doing things				
Feeling down, depressed, or hopeless				
Trouble falling or staying asleep, or sleeping too much				
Feeling tired or having little energy				
Poor appetite or overeating				
Feeling bad about yourself - or that you are a failure or have let yourself or your family down				
Trouble concentrating on things, such as reading the newspaper or watching television				
Moving or speaking so slowly that other people could have noticed? Or the opposite - being so fidgety or restless that you have been moving around a lot more than usual				
Thoughts that you would be better off dead or of hurting yourself in some way				

PHQ9 Score

.....

PHQ9 Q9 Alert Trigger

.....

	Not difficult at all	Somewhat difficult	Very difficult	Extremely difficult

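### One blank scoring item removes a participant's score for that measure, although questions may be left unanswered; no partial-score rule or item-nonresponse report is specified

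*Combined protocol and SAP*

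**What the plan says.** Three statements in the Data collection section of the Methods belong together.

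- Blanks are permitted: "REDCap survey settings allowed participants to skip some questions". The ground given is an IRB requirement that "participants were not obligated to answer any questions they felt uncomfortable with".
- The analysis set is complete-item: "only complete data sets were included for each outcome measure".
- The trigger and consequence are explicit: "if a participant omitted any subscale items necessary to calculate a total score", then "their data were excluded from the summary statistics and analyses for that measure".

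Under Aim 2, the indicator on adequacy of the outcome measures asks: "Are the measures acceptable, appropriate and relevant to the target population". The only completion statistic named sits under retention and is at survey level: "Survey completion rates by arm and timepoint".

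The document gives no rule for partially answered scales, no imputation, no sensitivity analysis, no missing-data assumption and no summary of item nonresponse. It also does not say whether exclusion covers one timepoint or all, whether a MAUQ domain score survives a blank in another domain, or whether a survey with blanks counts as completed.

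**The concern.** The design allows blanks because of what a question asks, and the analysis then drops the whole score when a blank occurs. Three things follow.

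- **Lost information.** A PHQ-9 with eight of nine symptom items answered contributes nothing.
- **Possible selection.** The document's own reason for blanks is discomfort. The clearest case is PHQ-9 item 9 in Appendix 1 ("Thoughts that you would be better off dead or of hurting yourself in some way"). If people with more severe symptoms skip it more often, the scores that remain come from a less severe group. Aim 3 uses these measures to obtain parameters for sizing a later trial, so a distorted mean or variance could carry forward.
- **A gap in Aim 2.** Item skipping is direct evidence on whether a measure is acceptable, yet nothing commits the study to reporting it. If a survey with blanks counts as completed, completion could look high while scale scores are missing.

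**Working it through.** The document states no sample size, dropout rate or item-skip rate, so there is no figure to reproduce. What follows is illustration with assumed inputs.

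**Inputs from the document.** Number of scoring items k:
- PROMIS Pain Interference 6b: 6.
- GAD-7: 7.
- PHQ-9: 9. The text calls it a 10-item form; Appendix 1 shows nine symptom items and one difficulty item, and I take the nine as scored.
- MAUQ: domains of 8, 6 and 7 items, 21 in all, given to the intervention arm at T2.

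**Assumed.** Each item is skipped independently with probability s = 1% or 2%.

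**Loss per visit** = 1 − (1 − s)^k.

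| Scale | k | s = 1% | s = 2% |
|---|---|---|---|
| PROMIS 6b | 6 | 1 − 0.99^6 = 5.9% | 1 − 0.98^6 = 11.4% |
| GAD-7 | 7 | 6.8% | 13.2% |
| PHQ-9 | 9 | 8.6% | 16.6% |
| MAUQ domain | 6 | 5.9% | 11.4% |
| MAUQ domain | 7 | 6.8% | 13.2% |
| MAUQ domain | 8 | 7.7% | 14.9% |
| MAUQ, single total | 21 | 19.0% | 34.6% |

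The last row applies only if one 21-item total is used. The document describes three domains and speaks of subscale items, so the domain rows are the safer guide.

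**Sensitivity to independence.** If the same few people leave every item blank, the loss is about s itself, 1–2%, whatever the scale length. The table is therefore towards the high end for these skip rates.

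**Possible bias in a PHQ-9 mean.** Suppose a share h of participants has a total D points higher and has its score excluded with probability q1, against q0 = 2% for the rest. Among complete scores the higher group's share becomes

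h' = h(1 − q1) / [h(1 − q1) + (1 − h)(1 − q0)],

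and the mean shifts by (h' − h) × D.

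- Mild case, h = 0.10, q1 = 0.10, D = 6: h' = 0.090 / (0.090 + 0.882) = 0.0926; shift −0.0074 × 6 = −0.04 points; 2.8% excluded.
- Strong case, h = 0.30, q1 = 0.40, D = 10: h' = 0.180 / (0.180 + 0.686) = 0.2079; shift −0.0921 × 10 = −0.92 points; 13.4% excluded.

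Over the assumed grid the mean is understated by 0.04 to 0.92 points. The between-arm difference is biased only if the pattern differs by arm.

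**What proration would recover.** With equal inter-item correlation r, a score prorated from k − 1 items correlates with the full score at

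sqrt{(k − 1)[1 + (k − 1)r] / (k[1 + (k − 2)r])}.

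For assumed r = 0.3 to 0.5 this is 0.973–0.986 (k = 6), 0.980–0.990 (k = 7) and 0.987–0.994 (k = 9). Little precision is lost per retained score when one item is missing.

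**The case against.** Complete-item scoring is disclosed and simple, and it can be defended in a feasibility study. Several stronger readings are tempting, and the document does not support them.

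- *One blank removes the participant from all four visits.* The sentence could be read so, but it does not say so. Data are collected by timepoint and completion is to be reported by timepoint, so exclusion per visit is at least as natural. This needs clarifying and supports no headline loss.
- *Any skipped question triggers exclusion.* Only items needed for a total score do. Open-text items, and the difficulty items if unscored, do not.
- *Skipping is invited, and missingness is not at random.* Skipping is allowed, and discomfort makes selective loss a foreseeable risk. No rate or pattern is reported to establish it.
- *The acceptability evidence is thrown away.* Exclusion is from a measure's statistics. Responses were extracted for analysis, so blanks should still be countable. What is missing is a commitment to report them.

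Two further objections stand. Proration fills a skipped item 9 from the other symptoms, so it does not cure bias when the item is skipped for its own content. And the document is written in the past tense with data already extracted, so a changed scoring rule may be post hoc. Whether each scoring guide permits proration cannot be checked here.

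These limit the size of the point and shape the remedy. They do not explain why no partial-score rule, sensitivity analysis or item-nonresponse summary is given.

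**Conclusion.** The point holds in limited form. The rule drops scores whose other items were answered, in a survey that permits blanks for discomfort, and Aim 2 has no item-level indicator for its own acceptability question.

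The per-visit losses calculated above rest on assumed 1–2% skip rates and independent skipping; clustering of skips in a few people would make them much smaller. Selective loss is plausible, most clearly for PHQ-9 item 9, but unproven. The change is worth making because it is cheap. The figures do not show that the results are wrong.

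**What to change.** 1. State that exclusion applies only to the affected visit and the affected scale or subscale, leaving the participant's other visits in the analysis.
2. Score a scale by proration when at least half of its items are answered (PROMIS by the missing-item method of its scoring manual), after checking each instrument's guide. Report these results beside the complete-item results. If the data have already been examined, label the prorated analysis post hoc.
3. Report item-level skip rates by measure, visit and arm as an Aim 2 result, and compare participants with and without complete scores. State whether a survey with blanks counts as completed.

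The cost is some scoring code, a check of the scoring guides and one or two tables from data already collected. Prorated scores carry slightly more measurement error. Because proration cannot remove content-driven bias, the skip table and the comparison in step 3 are needed alongside it.

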Appendix 1. Outcome measures

Eligibility Survey

What is your age?	 Younger than 18 years old  18-29  30-44  45-64  65 or older
What is your assigned sex at birth?	 Male  Female  Intersex
Which gender do you identify most with?	 Men  Women  Non-binary  Prefer to self-describe  Prefer not to answer
Please describe: -----	
Which of the following best describes you?	 American Indian or Alaskan Native  Asian American  Black or African American  Middle Eastern and/or North African decent  Native Hawaiian or Other Pacific Islander  White  Two or more races  Other  Prefer not to answer
Please specify: -----	
Are you of Hispanic or Latinx origin?	 Yes  No
How long have you been experiencing pain?	 Less than 3 months  3 months to 1 year  1 year-3 years  3 or more years

In the past 7 days, how much did pain interfere with...	Not at all	A little bit	Somewhat	Quite a bit	Very much
your enjoyment of life?					
your ability to concentrate?					
your day-to-day activities?					
your enjoyment of recreational activities?					
doing your tasks away from home (e.g., getting groceries, running errands)?					
How often did pain keep you from socializing with others?	 Never	 Rarely	 Sometimes	 Often	 Always

☐ 41.6

☐ 49.6

☐ 52.0

☐ 53.9

☐ 55.6

☐ 57.1

☐ 58.5

☐ 59.9

☐ 61.2

☐ 62.5

☐ 63.8

☐ 65.2

☐ 66.6

☐ 68.0

☐ 69.7

☐ 71.6

☐ 75.6

What number best describes your pain on average in the past 7 days?

No pain _____ Pain as bad as you can imagine

Do you have plans for inpatient surgery or surgery that requires hospitalization in the next three months?	 Yes  No
Are you pregnant?	 Yes  No
Are you currently being treated for cancer?	 Yes  No
Are you currently receiving hospice care?	 Yes  No

Do you have daily access to a smartphone and the Internet or a digital plan?	 Yes  No
It is easy for me to use mobile devices (e.g., mobile phone, tablets) to seek health information or services.	 Strongly disagree  Disagree  Somewhat disagree  Neutral  Somewhat agree  Agree  Strongly agree
I have the capability to use mobile devices to seek health information or services.	 Strongly disagree  Disagree  Somewhat disagree  Neutral  Somewhat agree  Agree  Strongly agree
I can use mobile devices to seek health information or services without much effort.	 Strongly disagree  Disagree  Somewhat disagree  Neutral  Somewhat agree  Agree  Strongly agree
How did you hear about our study?	 Phone calls  Mobile text messages (SMS)  Letter by mail  Email  Word-of-mouth (e.g., friends, colleagues, family)  Primary care providers  Other
Please describe	

Baseline Survey (T0)

What is the highest level of education you have completed?

- ☐ 8th grade or less
- ☐ Some high school, but did not graduate
- ☐ High school graduate or GED
- ☐ Some college but did not complete degree
- ☐ 2-year college degree
- ☐ 4-year college degree
- ☐ More than 4-year college degree

What is your current employment status?

- ☐ Full-time employed
- ☐ Part-time employed
- ☐ Contract/temporary
- ☐ Voluntarily unemployed
- ☐ Involuntarily unemployed
- ☐ Unable to work due to disability
- ☐ Retired

What is your current marital status?

- ☐ Never Married
- ☐ Living with a partner
- ☐ Married or civil union
- ☐ Separated
- ☐ Divorced
- ☐ Widowed

What is your annual household income in the past 12 months?

- ☐ Less than \$35,000
- ☐ \$35,000 to \$49,999
- ☐ \$50,000 to \$75,000
- ☐ More than \$75,000
- ☐ Don't know

Which type of health insurance do you now have?

- ☐ Private insurance
- ☐ Indian Health Service
- ☐ Medicare
- ☐ Medicaid
- ☐ Other government program (e.g., Marketplace)
- ☐ Others
- ☐ None or self-pay to receive medical care

Please specify:

What is your living situation today?

- ☐ I have a steady place to live
- ☐ I have a place to live today, but I am worried about losing it in the future
- ☐ I do not have a steady place to live

In the past month, how often was the following true: "You worried that your food would run out before you got money to buy more."

- ☐ Often true
☐ Sometimes true
☐ Never true

In the past month, has the electric, gas oil, or water company shut off service or threatened to shut off service in your home?

- ☐ No
☐ Threatened to shut off service
☐ Already shut off service

In the past month, has lack of reliable transportation kept you from medical appointments, meetings, work, or from getting to things needed for daily living? (Check all that apply)

- ☐ No
☐ Yes, it has kept me from non-medical meetings/appointments, work, or getting things that I need
☐ Yes, it has kept me from medical appointments or getting medication

What types of treatment do you currently receive for pain? (Check all that apply)

- ☐ Medications
☐ Outpatient procedures (e.g., epidurals or other injections)
☐ Behavioral health service or therapy
☐ Physical therapy
☐ Massage
☐ Acupuncture
☐ Yoga
☐ Mindfulness
☐ Dietary changes
☐ Exercise
☐ Mobile apps (other than the 2Morrow chronic pain program)
☐ Others
☐ None

Please specify which medications:

Please specify which other treatments:

In the past 7 days, how much did pain interfere with...					
	Not at all	A little bit	Somewhat	Quite a bit	Very much
your enjoyment of life?					
your ability to concentrate?					
your day-to-day activities?					
your enjoyment of recreational activities?					
doing your tasks away from home (e.g., getting groceries, running errands)?					

	Never	Rarely	Sometimes	Often	Always
How often did pain keep you from socializing with others?					

Over the last 2 weeks, how often have you been bothered by any of the following problems?

	Not at all	Several days	More than half the days	Nearly every day
Little interest or pleasure in doing things				
Feeling down, depressed, or hopeless				
Trouble falling or staying asleep, or sleeping too much				
Feeling tired or having little energy				
Poor appetite or overeating				
Feeling bad about yourself - or that you are a failure or have let yourself or your family down				
Trouble concentrating on things, such as reading the newspaper or watching television				
Moving or speaking so slowly that other people could have noticed? Or the opposite - being so fidgety or restless that you have been moving around a lot more than usual				
Thoughts that you would be better off dead or of hurting yourself in some way				

PHQ9 Score

.....

PHQ9 Q9 Alert Trigger

.....

	Not difficult at all	Somewhat difficult	Very difficult	Extremely difficult
If you checked off any problems, how difficult have these problems made it for you to do your work, take care of things at home, or get along with other people?				

Over the last 2 weeks, how often have you been bothered by any of the following problems?	Not at all	Several days	More than half the days	Nearly every day
Feeling nervous, anxious or on edge				
Not being able to stop or control worrying				
Worrying too much about different things				
Trouble relaxing				
Being so restless that it is hard to sit still				
Becoming easily annoyed or irritable				
Feeling afraid as if something awful might happen				
	Not difficult at all	Somewhat difficult	Very difficult	Extremely difficult
If you checked off any problems, how difficult have these problems made it for you to do your work, take care of things at home, or get along with other people?				

What number best describes your pain on average in the past 7 days? (0 = No pain, 10 = pain as bad as you can imagine)

No pain _____ Pain as bad as you can imagine

1-Month, 3-Month and 6-Month Follow-up Survey

Includes the Salty for Chronic Pain Questionnaire for Intervention Arm

In the past 7 days, how much did pain interfere with...	Not at all	A little bit	Somewhat	Quite a bit	Very much
your enjoyment of life?					
your ability to concentrate?					
your day-to-day activities?					
your enjoyment of recreational activities?					
doing your tasks away from home (e.g., getting groceries, running errands)?					

	Never	Rarely	Sometimes	Often	Always
How often did pain keep you from socializing with others?					

Over the last 2 weeks, how often have you been bothered by any of the following problems?

	Not at all	Several days	More than half the days	Nearly every day
Little interest or pleasure in doing things				
Feeling down, depressed, or hopeless				
Trouble falling or staying asleep, or sleeping too much				
Feeling tired or having little energy				
Poor appetite or overeating				
Feeling bad about yourself - or that you are a failure or have let yourself or your family down				
Trouble concentrating on things, such as reading the newspaper or watching television				
Moving or speaking so slowly that other people could have noticed? Or the opposite - being so fidgety or restless that you have been moving around a lot more than usual				
Thoughts that you would be better off dead or of hurting yourself in some way				

	Not difficult at all	Somewhat difficult	Very difficult	Extremely difficult
If you checked off any problems, how difficult have these problems made it for you to do your work, take care of things at home, or get along with other people?				

PHQ9 Q9 Alert Trigger

PHQ9 Q9 Alert Trigger

PHQ9 Q9 Alert Trigger

Over the last 2 weeks, how often have you been bothered by any of the following problems?

	Not at all	Several days	More than half the days	Nearly every day
Feeling nervous, anxious or on edge				
Not being able to stop or control worrying				
Worrying too much about different things				
Trouble relaxing				
Being so restless that it is hard to sit still				
Becoming easily annoyed or irritable				
Feeling afraid as if something awful might happen				

GAD7 Score Questions 1-7

	Not at all	Somewhat difficult	Very difficult	Extremely difficult
If you checked off any problems, how difficult have these problems made it for you to do your work, take care of things at home, or get along with other people?				

GAD7 Score Total

What number best describes your pain on average in the past 7 days? (0 = No pain, 10 = pain as bad as you can imagine)

No pain _____ Pain as bad as you can imagine

Have you visited primary care for pain during the past month?	 Yes  No
Have you engaged with the content of the 2Morrow chronic pain app program during the past month?	 Yes  No

What types of treatment have you received for pain during the past month?

(Check all that apply)

- ☐ Medications
- ☐ Outpatient procedures (e.g., epidurals or other injections)
- ☐ Behavioral health service or therapy
- ☐ Physical therapy
- ☐ Massage
- ☐ Acupuncture
- ☐ Yoga
- ☐ Mindfulness
- ☐ Dietary changes
- ☐ Exercise
- ☐ Mobile apps (other than the 2Morrow chronic pain program)
- ☐ Others
- ☐ None

Please specify which medications

Please describe what other treatments you have received

The next questions relate to the Salty Program for Chronic Pain that you used while participating in this study.

	Not at all	Slightly	Moderately	Very	Extremely
The Salty Program helped me with my pain, for example, to better understand or manage my pain.					
Was using the Salty program worth your time?					

What did you like or find most helpful about the Salty program?

What did you like or find most helpful about the Salty program?

What would you like to see improved or added to the Salty program?

How likely are you to recommend the Salty Program to others experiencing chronic pain?

- ☐ 0 - Not at all
- ☐ 1
- ☐ 2
- ☐ 3
- ☐ 4
- ☐ 5
- ☐ 6
- ☐ 7
- ☐ 8
- ☐ 9
- ☐ 10 - Extremely likely

Please rate how helpful the following features in the Salty Program were to you.

	Not at all	Slightly	Moderately	Very	Extremely
The lessons and content in the program					
Having the program divided into different topics ranging from physical, emotional, social aspects of pain					
Having content related to how pain may affect you physically					
Having content related to how pain may affect you emotionally					
Having content related to how pain may affect you socially					
How much you got to do each day					
Having to complete an entire section of lessons before moving to other topics or themes					
Daily check-ins to track how things are going for you					
Viewing insights from daily tracking					
The option to connect with a coach					
Earning passport stamps					
Opportunity to receive a Fitbit					
Seeing Fitbit data in the app					
Length of the program (100 days)					
Self-discovery surveys in the app to learn more about your mood, drinking, etc.					
Videos that you watched					
Other					

What other features were helpful to you?

Looking back to your use of the Salty program, what did you learn that may have changes the way you think about or manage your pain?

Health Care Resource Utilization (HCRU) Survey

During the past 3 months, did you receive any care, treatments, or tests for your chronic pain?

- ☐ No
☐ Unsure
☐ Yes
☐ Prefer not to say

This may include seeing or talking with a doctor or health professional, having laboratory tests, x-rays or other imaging, receiving treatment procedures, seeing an acupuncturist, massage or physical therapist, or some other care for your chronic pain.

In the past 3 months, do you think any of the following improved?

Satisfaction with my chronic pain care: _____
The communication with my providers about my pain and treatment: _____
Feeling more involved in my pain care: _____
Amount of pain care received (doctor visits, tests, procedures, etc): _____

Check all that apply

- ☐ More emergency room visits
☐ More urgent care visits
☐ More doctor visits (in person or virtually)
☐ More treatment procedures
☐ More tests
☐ More something else

Check all that apply

- ☐ Fewer emergency room visits
☐ Fewer urgent care visits
☐ Fewer doctor visits (in person or virtually)
☐ Fewer treatment procedures
☐ Fewer tests
☐ Fewer something else

mHealth App Usability Questionnaire

Ease of Use and Satisfaction							
	Strongly Disagree	Disagree	Somewhat Disagree	Neither Agree or Disagree	Somewhat Agree	Agree	Strongly Agree
The app was easy to use.							
It was easy for me to learn to use the app.							
I like the interface of the app.							
The information in the app was well organized, so I could easily find the information I needed.							
I feel comfortable using this app in social settings.							
The amount of time involved in using this app has been fitting for me.							
I would use this app again.							
Overall, I am satisfied with this app.							

System information arrangement							
	Strongly Disagree	Disagree	Somewhat Disagree	Neither Agree or Disagree	Somewhat Agree	Agree	Strongly Agree
Whenever I made a mistake using the app, I could recover easily and quickly.							
This mHealth app provided an acceptable way to receive health care services.							
The app adequately acknowledged and provided information to let me know the progress of my action.							
The navigation was consistent when moving between screens.							

The interface of the app allowed me to use all the functions (such as entering information, responding to reminders, viewing information) offered by the app.

☐ ☐ ☐ ☐ ☐ ☐ ☐ ☐

This app has all the functions and capabilities I expect it to have.

☐ ☐ ☐ ☐ ☐ ☐ ☐ ☐

Usefulness							
	Strongly Disagree	Disagree	Somewhat Disagree	Neither Agree or Disagree	Somewhat Agree	Agree	Strongly Agree
The app would be useful for my health and well-being.							
The app improved my access to health care services.							
The app helped me manage my health effectively.							
The app made it convenient for me to communicate with my health care provider.							
Using the app, I had many more opportunities to interact with my health care provider.							
I felt confident that any information I sent to my provider using the app would be received.							
I felt comfortable communicating with my health care provider using the app.							
